1 INTRODUCTION

1.1 Background

As of November 23, 2020, Centers for Disease Control and Prevention (CDC) received 12,175,921 COVID-19 case reports for the United States (U)S since January 22, 2020. There were slightly more women (52%) than men (48%) included in these reports (1). The most recent tracking data from CDC includes 39,857 case reports of US pregnant women with COVID-19 received between January 22 and November 23, 2020, with 53 deaths and 8,284 hospitalizations, although these data did not distinguish between hospitalization for COVID-19 conditions from admissions for pregnancy-related indications, such as delivery. The race/ethnicity breakdown of the pregnancy COVID-19 cases was 37% Hispanic, 35% White Non-Hispanic, 19% Black Non-Hispanic, 3%, Asian and 6% Multiple/Other (2). In an earlier MMWR publication describing the period between January 22 and June 7, 2020, CDC reported receiving notifications of 326,335 women of reproductive age (15-44 years) with positive SARS-CoV-2 test results. Of the 91,412 of these women with pregnancy data, 9% (8,207) were pregnant. Hospitalization was reported in 31.5% of pregnant women compared to 5.8% of nonpregnant women but the data did not distinguish between hospitalization for COVID-19 conditions from admissions for pregnancy-related indications, such as delivery. After adjusting for age, presence of underlying medical conditions, and race/ethnicity, pregnant women were significantly more likely to be hospitalized (aRR = 5.4, 95%) confidence interval [CI] = 5.1-5.6), to be admitted to the intensive care unit (ICU) (aRR = 1.5, 95% CI = 1.2–1.8) and to receive mechanical ventilation (aRR = 1.7, 95% CI = 1.2–2.4) than nonpregnant women (3). Increased need for intensive care during pregnancy has also been reported in Swedish women with COVID-19 (4). A review of published data on severe coronavirus infections in pregnancy reported adverse pregnancy outcomes, including maternal death, preterm delivery, stillbirth and neonatal death, as well as respiratory compromise requiring ICU care and mechanical ventilation, in pregnant women with COVID-19, although at lower frequency than with MERS-CoV and SARS-CoV-1 (5).

Despite this reported incidence of severe COVID-19 in pregnant women associated with adverse pregnancy and maternal health outcomes, pregnant women are routinely excluded from participation in research protocols within COVID-19 drug development programs(6). The physiological changes associated with pregnancy can have a dramatic impact on drug disposition and use of therapeutic agents during pregnancy poses unique safety concerns(6). As a result, drugs cannot be used safely and effectively during pregnancy without their pharmacokinetics (PK) and safety being evaluated in pregnant women. Only a few of the many COVID-19 clinical treatment trials currently listed on clinicaltrials.gov include pregnant women(7). Those that do involved use of hydroxychloroquine, which has been used extensively in pregnant women for malaria treatment but is no longer recommended for routine use in treatment of COVID-19 due to a lack of proven efficacy in the presence of significant risk of major toxicity(8).

Remdesivir (GS-5734TM) (RDV), a nucleotide prodrug originally developed for the treatment of Ebola virus disease and Marburg virus infections, is the first drug licensed for use against COVID-19, the disease caused by infection with SARS-CoV-2 virus(9). RDV has been shown to shorten time to recovery from severe COVID-19 (10-12). In an activation process analogous to that of tenofovir alafenamide (TAF) and sofosbuvir (SOF), RDV is metabolized to an intracellular nucleotide triphosphate which inhibits viral RNA polymerases. Now that RDV is licensed, hospitalized pregnant women with COVID-19 can receive RDV part of clinical care; however, since all RDV research protocols excluded pregnant women there are no RDV pregnancy PK data and only limited RDV in pregnancy safety data from observational cohorts(13).

The routine exclusion of pregnant women from drug development programs results in therapeutic agents typically being licensed for use in non-pregnant adults in the absence of pregnancy specific PK and safety

data. As a result, these licensed drugs cannot be employed with evidence-based certainty as to their safety and efficacy in pregnant women until data are available from the requisite pregnancy PK and safety studies, which often require years to complete. Requisite PK and safety studies require years to complete. As an example, it took 3-5 years after licensure of cobicistat before its failure as an effective booster of elvitegravir and darunavir in pregnant women was recognized and warnings against its use in pregnancy were issued, during which time cobicistat was used routinely as part of clinical care for pregnant women living with HIV(6). A similar delay in the availability of pregnancy PK and safety data for drugs shown to be effective against COVID-19 would be tragic, given the incidence, acuity and observed severity of COVID-19 in pregnant women and the current paucity of proven effective therapies.

1.2 Clinical Pharmacology During Pregnancy

RDV is the first drug with preliminary evidence of efficacy in COVID-19(14). RDV is a prodrug that requires several steps of metabolism to generate its active intracellular nucleotide triphosphate (NTP, GS-443902), following a similar activation sequence as SOF (Figure 2). RDV is a monophosphoramidate

prodrug of an adenosine analog that is made more lipophilic by the addition of alkyl-alanine and phenyl phosphate esters. RDV is rapidly converted by plasma and liver hydrolases to a nucleoside analog monophosphate. Inside cells the nucleoside analog monophosphate is rapidly converted to the active triphosphate form (GS-443902), which competes with natural adenosine triphosphate (ATP) to selectively inhibit RNA-dependent RNA polymerase. Dephosphorylation of the nucleoside analog results in GS-441524, which is not as efficiently rephosphorylated as RDV.

Remdesivir

Sofosbuvir

Sofosbuvir

Wey: nucleoside analog with monophosphoramidate moiety (blue box) attached to alanine alkyl ester (red box) and phenyl ester (green box). Structures from https://pubchem.ncbi.nlm.nih.gov/.

The in vitro EC50 against SARS-CoV-2 has been reported at 0.137 μ M (83 ng/mL) and 0.77 μ M (460 ng/mL) in Vero cells (11, 15). In a human lung epithelial cell line (Calu3), in vitro EC50s for RDV and GS-441524 were 0.28 uM (169 ng/mL),and 0.62 uM (181 ng/mL) by plaque assay. RDV demonstrated greater potency in human airway epithelial cells

with an EC50 of 0.01 uM (6 ng/mL), likely due to higher GS-443902 concentrations in HAE cells in comparison to the Calu-3 and Vero E6 cell types. Due to poor hepatic stability, RDV should not be given orally as bioavailability is expected to be low. RDV PK data at the currently recommended doses for COVID-19 treatment are primarily limited to healthy non-pregnant adults studied in preparation for studies of RDV use against Ebola(16). See Table 1 below for summary plasma PK parameters. In this study, Day 1 peak plasma concentrations after a 200 mg intravenous (IV) dose administered over 30 minutes were 9.0 μM (5440 ng/mL) for RDV and 0.5 μM (152

[figure not shown]

Figure 3: Expected RK for Remotestivinand SS-444224 and

ng/mL) for GS-441524. AUC $_{0.24h}$ were 4.8 μ M-h (2920 ng*h/mL) for RDV and 7.7 μ M-h (2240 ng*h/mL) for GS-441524 (15). Sparse PK results in a 66 year old female and a 67 year old male with COVID-19 have also been detailed(17). Median peak RDV concentrations of 4.54 uM (2737 ng/mL) and

5.50 uM (3317 ng/mL) were measured in each of these patients, respectively, on infusion Days 3-9. GS-441524 AUC_{0-24h} was 10.7 uM-h (3117 ng*h/mL) in the male patient, and 21.1 uM-h (6131 ng*h/mL) in the female patient, who had 1.96-fold higher levels due to underlying renal dysfunction.

No accumulation of RDV occurred with multiple dosing, consistent with its measured half-life in plasma of just under 1 hour. Following single doses ranging from 3 – 225 mg IV, PK of GS-441524 were linear. GS-441524 reaches steady-state in 4 days and accumulated 1.9-fold based on AUC, consistent with its ~24-hour half-life. The intracellular phosphorylated metabolite GS-443902 has a median half-life of 32.23 to 48.38 hours. Renal and biliary excretion were the major routes of elimination in rats and monkeys.(15) In the mass balance study, mean total recovery of the dose was greater than 92%, consisting of approximately 74% recovered in urine and 18% recovered in feces. The majority of the IV RDV dose recovered in urine was the GS-441524 metabolite (49%) followed by RDV (10%) and other metabolites(18). The impact of pregnancy on hydrolase activity and RDV PK is unknown. A simulation from modelling based on pregnancy PK data for other renally eliminated drugs is presented in Figure 3 (19-22). The modelling and simulation suggest that increased glomerular filtration rate (GFR) and renal tubular secretion associated with pregnancy will increase GS-441524 elimination. Because RDV is 88-94% protein bound, while its metabolites are only 1-2% protein bound (9), pregnancy related changes in plasma protein concentrations due to volume expansion and drug displacement from protein binding sites may also affect unbound RDV concentrations.

Table 1. Plasma PK Parameters of RDV and GS-441524 Following 30-minute IV Infusion(s) of RDV 200 mg on Day 1 and 100 mg Daily on Days 2-5 in Healthy Adults (Preliminary Analysis)(15)

PK Parameter	Remdesivir		GS-441524	
	Day 1 (n=8)	Day 5 (n=7)	Day 1 (n=8)	Day 5 (n=7)
Cmax (ng/mL)	5440 (20.3)	2610 (12.7)	152 (25.9)	142 (30.3)
AUC (hr*ng/mL)	2920 (20.6)	1560 (13.9)	2240 (29.1)	2230 (30.0)
T _{1/2} (h)	0.98 (0.82, 1.03)	0.89 (0.82, 1.09)	NA	25.3 (24.10, 30.32)

C_{max} and AUC summarized as geometric mean (CV%); t_{1/2} summarized as median (Q1, Q3)

RDV is currently licensed for use in adults and pediatric patients (12 years of age and older and weighing at least 40 kg) for the treatment of coronavirus disease 2019 (COVID-19) requiring hospitalization(9). The only RDV PK data currently available are from healthy non-pregnant adult volunteers, for which results by sex were not detailed, and sparse PK results from two patients with COVID-19(9, 16, 17). No data describing RDV PK in pregnant women or non-pregnant women with COVID-19 are available. Clinical data with RDV use in pregnancy are limited to the experience of 6 pregnant women in the Democratic Republic of Congo who received RDV as Ebola treatment and 67 pregnant and 19 postpartum women who received remdesivir for COVID-19 under the Gilead compassionate use protocol(13, 23). Remdesivir was well tolerated by the pregnant women treated for Ebola (23). The pregnant and postpartum women who received RDV for COVID-19 under the Gilead compassionate use protocol all had room air oxygen saturation 94% or lower. There was one spontaneous miscarriage and one postpartum women who died but no pregnant woman or live born infant died. None of the pregnant women developed gestational hypertension or pre-eclampsia. Ninety three percent of pregnant women and 89% of postpartum women recovered from COVID-19. Serious adverse events (SAEs) were observed in 29% of women, including deep vein thrombosis, hypertension, hypoxia and pleural effusion. Elevations of laboratory parameters were common, occurring in 67% (13).

The use of RDV in pregnant women in the absence of PK and safety data places pregnant women receiving RDV at risk for both inadequate therapeutic response and unrecognized maternal toxicity including adverse pregnancy outcomes.

1.3 Rationale

Although pregnant women are routinely excluded from COVID-19 experimental treatment protocols, the care providers of pregnant women who develop severe COVID-19 are treating them with potential therapies in the absence of pregnancy specific PK and safety data and outside of research protocols. Under these circumstances, the fastest way to get the urgently needed RDV pregnancy PK and safety data is through an opportunistic RDV PK and safety protocol in pregnant women receiving RDV as part of clinical care. IMPAACT 2032 will follow the opportunistic design of the highly successful IMPAACT P1026s study which between 2004 and 2019 performed intensive PK sampling and safety evaluations for HIV and TB therapeutics in over 1000 pregnant and postpartum women, successfully evaluating the PK and safety of over 25 different HIV and TB medications in pregnant and postpartum women. Because of the duration of treatment of HIV and TB, participants in IMPAACT P1026s were studied both during pregnancy and postpartum, serving as their own controls. This approach is not possible with RDV, which has a treatment duration of 5-10 days. As a result, women treated during pregnancy will generally not be receiving the drug postpartum. Under these circumstances the best comparison group for PK and safety data from pregnant women would be data from non-pregnant adult women of childbearing potential. Since such data are lacking for RDV, IMPAACT 2032 will also simultaneously enroll and study RDV PK and safety in a cohort of COVID-19 positive, non-pregnant women of childbearing potential. These nonpregnant participants will provide the first data describing RDV PK and safety in women receiving RDV for COVID-19 and will serve as a comparison group for the IMPAACT 2032 pregnant women.

The recent recognition of the acuity and severity of COVID-19 in pregnant women mandates rapid development of a streamlined protocol that can be implemented with minimal delay to provide the critical RDV pregnancy specific PK and safety data needed to allow RDV to be used safely and effectively in pregnant women. This protocol was designed with recognition of the challenges posed by performing a research protocol on hospitalized participants acutely ill with COVID-19 during an ongoing and rapidly changing pandemic. Priority has been given to obtaining the urgently needed pregnancy RDV PK and safety data as quickly as possible through protocol activities that pose the least risk of violating RDV infection control measures, to avoid putting clinical staff, research staff and other hospital patients at increased risk of SARS-CoV-2 infection. The protocol team has endeavored to develop a protocol that will acquire RDV PK and safety data in pregnant women as quickly, efficiently and safely as possible under these challenging conditions. The team has elected to design the study to facilitate ease and practicality of implementation and to focus on acquiring only those data necessary to provide an initial evidence base for the use of RDV in pregnant women. This approach is reflected in many aspects of the protocol, including the eligibility criteria, participant data collection procedures, PK sampling and analysis approach, and duration of follow up.

IMPAACT 2032 will provide critical RDV PK and safety data in women, allowing evaluations of exposure of RDV and its metabolites in both pregnant and non-pregnant adult women and of RDV safety when used in these populations. This protocol will provide urgently needed RDV PK and safety data in women with COVID-19, providing evidence necessary to ensure that RDV can be used safely and effectively in both pregnant and non-pregnant women of childbearing potential.

2 OBJECTIVES

2.1 Primary Objectives

The primary objectives of this study are to:

- **2.1.1** Arm 1: Describe the pharmacokinetics of RDV and its metabolite, GS-441524, after administration to pregnant women as part of clinical care.
- 2.1.2 Arm 1: Describe the clinical and laboratory safety outcomes through four weeks post-last infusion and during delivery in pregnant women receiving RDV as part of clinical care.

2.2 Secondary Objectives

The secondary objectives of this study are to:

- **2.2.1** Arm 2: Describe the pharmacokinetics of RDV and its metabolite, GS-441524, after administration to non-pregnant women of childbearing potential as part of clinical care.
- 2.2.2 Arm 2: Describe clinical and laboratory safety outcomes through four weeks post-last infusion in non-pregnant women of childbearing potential receiving RDV as part of clinical care.

2.3 Other Objectives

The other objectives of this study are to:

- 2.3.1 Arm 1: Describe RDV placenta transfer with collection of plasma and cord blood samples at delivery in mothers who have received a dose of RDV within the preceding 5 days.
- **2.3.2** Arms 1 and 2: Compare the pharmacokinetics of RDV and its metabolite, GS-441524, in pregnant women to those observed in non-pregnant women of childbearing potential.
- 2.3.3 Arms 1 and 2: Describe and compare intracellular concentrations of RDV's active intracellular nucleotide triphosphate (GS-443902) in pregnant and non-pregnant women of childbearing potential receiving RDV as part of clinical care.
- **2.3.4** Arms 1 and 2: Develop a population PK (PopPK) model of RDV and its metabolites in pregnant and non-pregnant women receiving RDV and evaluate associations between clinical characteristics and RDV and GS-441524 pharmacokinetics.
- **2.3.5** Arms 1 and 2: Assess plasma protein binding of RDV in pregnant women and non-pregnant women of child-bearing potential.
- **2.3.6** Arms 1 and 2: Describe the frequency of detection in breast milk and the relative concentrations in breast milk and plasma of RDV and GS-441524 in lactating women undergoing RDV PK sampling.

.

3 STUDY DESIGN

This is a Phase IV prospective, open label, non-randomized opportunistic study to evaluate the PK and safety of RDV when administered to pregnant and non-pregnant women of childbearing potential for treatment of COVID-19. RDV is not provided as part of this study; a requirement for entry is that participants receive RDV as part of their clinical care (i.e., outside of the study). Participation in this study will have no effect on the cost of care for treatment of COVID-19 or the cost of any RDV received for clinical care. Information on patient support for access to RDV can be found at https://www.vekluryhcp.com/patient-support/. As no investigational drug is being provided to study participants, the study is opportunistic in nature and clinical care decisions are made outside the context of this study, and as the Division of AIDS (DAIDS) at the US National Institutes of Health (NIH), as the study sponsor, is not charging for use of RDV in the context of this study, 21 CFR 312.8 is not applicable to this study.

A target of 20 PK evaluable pregnant women will be enrolled into Arm 1; a target of 20 PK evaluable non-pregnant women of childbearing potential will be enrolled into Arm 2. See Section 10.2 for a definition of PK evaluable. Refer to Sections 4.1 through 4.3 for the eligibility criteria and to Section 4.5 for a description of the recruitment, screening and enrollment process. Study sites will be located in the United States.

Participants will be pregnant and non-pregnant women hospitalized for COVID-19 and will receive daily RDV infusions, typically for 5 days but in some cases for up to 10 days, as part of their clinical care. RDV will be provided and managed by the participants' treating physician and will not be provided as a part of this study. Women may be enrolled prior to starting RDV or after starting RDV but must be enrolled prior to the start of the 4th infusion. Participants will undergo intensive PK sampling on the day of the 3rd, 4th, or 5th infusion (at site discretion), as described in Section 6.4.1. Protein binding capacity of RDV will also be assessed ex vivo from the pre-dose intensive PK sample. Participants will also undergo collection of single PK samples with standard of care (SOC) labs drawn on the days of the 2nd, 3rd, 4th, and 5th infusions (with the exception of the day of intensive PK sampling), and also at 48 hours after the last infusion, as described in Section 6.4.2. For Arm 1 participants, maternal and cord blood PK sampling will be performed at delivery for a comparison of maternal and fetal plasma RDV concentrations if the participant received RDV infusion within the preceding 5 days. Additionally, for women in both Arms who are lactating, and who consent to this sample collection, an optional breast milk sample may be collected on the intensive PK sampling day and at 48-hours after the last RDV infusion, to assess breast milk concentrations of RDV and its metabolites.

For all women, clinical and laboratory evaluations will be abstracted from the medical record. Pregnancy, birth, and infant outcomes will be obtained from pregnant women enrolled in Arm 1. See Appendix I and Section 6 for additional details. Arm 1 and Arm 2 participants will be followed through 4 weeks after the last infusion of RDV; Arm 1 women who are still pregnant at that time will have additional follow-up at the time of delivery.

4 STUDY POPULATION

This study will be conducted among hospitalized pregnant and non-pregnant women receiving RDV infusion for treatment of COVID-19 as part of their clinical care (i.e., not as part of this study). Women will be assessed for eligibility per the criteria specified in Sections 4.1 through 4.3, and the requirements in Section 4.4. The study-specific approach to recruitment, screening, and enrollment is described in Section 4.5. Considerations related to participant retention and withdrawal/discontinuation from the study are provided in Sections 4.6 and 4.7, respectively.

4.1 Inclusion Criteria – Arm 1 (Pregnant Women)

Women must meet all of the following inclusion criteria to be enrolled in Arm 1.

4.1.1 Of legal age or otherwise able to provide independent informed consent as determined by site SOPs and consistent with all applicable IRB policies and procedures, and is willing and able to provide informed consent for her own participation in this study.

Or

Of legal age to provide independent informed consent but is unable to provide informed consent (e.g. impaired capacity, as determined by site SOPs and consistent with all applicable IRB policies and procedures) and a Legally Authorized Representative (LAR) is willing and able to provide written informed consent on behalf of the participant in accordance with 21 CFR 50.27.

Note: All sites must follow the policies and procedures of all applicable IRBs; this includes single IRB (sIRB) policies and procedures. Refer to Section 13.1 for more information on sIRB oversight.

- **4.1.2** At study entry, viable intra-uterine pregnancy of any gestational age, based on medical records.
- **4.1.3** At study entry, hospitalized AND has confirmed or suspected COVID-19, based on medical records.
- **4.1.4** At study entry, receiving or expected to receive RDV for COVID-19 clinical care, as prescribed by the clinical care provider and documented in medical records.

Note: The study investigator or designee will confirm that a potential study participant is receiving or expected to receive RDV based on information in the medical record.

4.2 Inclusion Criteria – Arm 2 (Non-Pregnant Women)

Women must meet all of the following inclusion criteria to be enrolled in Arm 2.

4.2.1 Of legal age or otherwise able to provide independent informed consent as determined by site SOPs and consistent with all applicable IRB policies and procedures, and is willing and able to provide informed consent for her own participation in this study.

Or

Of legal age to provide independent informed consent but is unable to provide informed consent (e.g. impaired capacity, as determined by site SOPs and consistent with all applicable IRB policies and procedures) and a LAR is willing and able to provide written informed consent on behalf of the participant in accordance with 21 CFR 50.27.

Note: All sites must follow the policies and procedures of all applicable IRBs; this includes sIRB policies and procedures. Refer to Section 13.1 for more information on sIRB oversight.

- **4.2.2** At study entry, between 18 and 45 years of age, based on medical records and participant report.
- **4.2.3** Assigned female at birth and at study entry not taking cross-sex hormone therapy.
- **4.2.4** At study entry, not suspected to be pregnant, based on participant report and/or investigator or designee determination.
- **4.2.5** At study entry, hospitalized AND has confirmed or suspected COVID-19, based on medical records.
- **4.2.6** At study entry, receiving or expected to receive RDV for COVID-19 clinical care, as prescribed by the clinical care provider and documented in medical records.

Note: The study investigator or designee will confirm that a potential study participant is receiving or expected to receive RDV based on information in the medical record.

4.3 Exclusion Criteria – Arms 1 and 2

Women who meet any of the following criteria will be excluded from enrolling in this study:

- **4.3.1** At study entry, has started or received the 4th RDV infusion.
- **4.3.2** At study entry, evidence of post-menopausal status (medical or surgical), based on medical records and/or participant report.
- **4.3.3** At study entry, any contraindications to RDV treatment for COVID-19, based on investigator or designee determination.
- **4.3.4** Received or administered any disallowed medications listed in Section 5.4 within 48 hours prior to study entry.
- **4.3.5** At study entry, has any other condition, that, in the opinion of the site investigator or designee, would make participation in the study unsafe, complicate interpretation of study outcome data, or otherwise interfere with achieving study objectives.

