6.3 Pre-infusion

The Pre-infusion period is defined as 48-hours priors to initiation of RDV infusions for COVID-19. Clinical and laboratory data will be collected per Table 2 for this time period (unless alternate time period is specified for specific data elements). If Screening/Entry occurs within or after 48-hours prior to the first RDV infusion, the clinical and laboratory data for the Pre-infusion period will be collected retrospectively after study entry.

Table 2: Data Collection Requirements for Pre-infusion Period

Evaluation	Enter into eCRFs or SES	
Medical History	 Record the following as available in the medical records: All medical conditions of any grade occurring or ongoing within 48 hours prior to the first infusion of RDV. These will be considered preexisting conditions and unrelated to RDV. Arm 1: Major obstetrical diagnoses during the current pregnancy prior to start of RDV infusions Arm 1: Gestational age at 48 hours prior to first infusion. Arm 1: Prior pregnancy information (number and dates of prior pregnancies, outcome of prior pregnancies) Last menstrual period 	

Evaluation	Enter into eCRFs or SES
	 Hospitalization for COVID-19 (COVID-19 status at hospitalization, COVID-19 symptoms onset date, hospitalization onset date, discharge date)
Concomitant Medications	Record the following medications available in the medical records EXCEPT RDV: • All prescription medications • Blood products and transfusions • All investigational drugs
Vital Signs	Record the following measurements that are available in the medical records: Record only once: Height Weight Record the most abnormal measurement in a 24-hour period: Highest systolic blood pressure Temperature Pulse rate Pulse oximetry
Respiratory Status	Record the respiratory and/or ventilation status

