6.5.2 Breast Milk Sample Collection at 48-Hours Post Last Infusion

At the 48-Hour Post Last Infusion data collection timepoint **only**, an optional breast milk sample will be collected from postpartum lactating women who are still hospitalized and who consented to provide a breast milk sample.

Breast milk samples may be collected within a window of +/- 12 hours of the 48-Hour Post Last Infusion timepoint. If possible, collection of breast milk should be targeted to within 90-minutes on either side of the 48-Hour Post Last Infusion single plasma PK sample collection. If circumstances do not permit collection of the breast milk sample within +/-12-hour window (e.g., breast pump not permitted in participant room due to infection control measures, participant too sick to express milk), collection of this sample may be omitted. The date and time of breast milk sample collection will be source documented and entered into eCRFs. See the LPC for processing instructions.

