9.6 Analyses

This section provides a brief summary of the planned statistical analyses. Details will be specified in a separate, comprehensive SAP. Section 10.4 describes the pharmacology data analyses and modelling, including the non-compartmental and population PK analyses.

The data analyses to address the primary and secondary PK and safety objectives will include descriptive statistics. PK outcome measures will be summarized using geometric means, arithmetic means, % CVs, and 90% CIs. The 90% CI for the arithmetic mean will be calculated on the log scale using the modified Cox approach(24). Continuous safety outcome measures, such as newborn birth weight, will be summarized using mean and median as measures of location and the standard deviation and quantiles of minimum, 25th percentile, 75th percentile, and maximum as measures of dispersion. Categorical safety outcome measures will be summarized using proportions and exact binomial (Clopper-Pearson) 95% CIs. Descriptive statistics will also be presented by trimester for Arm 1

For the objectives that compare PK parameters between arms, 90% CIs for the geometric mean ratio (GMR) of the PK parameters in study pregnant women versus non-pregnant women will be calculated to assess whether or not there is a greater than 30% difference in exposure in pregnant women versus non-pregnant women. The confidence coefficient will be 90% rather than 95% to match the usual practice in the PK literature. We will use Schuirmann's two one-sided tests (TOST) approach to show that the means of the two groups do not differ by more than the 30% margin of equivalence, i.e.: the 90% CI of the GMR is between 0.7 and 1.43(26). As discussed in Section 9.1, the 30% margin is a preliminary analysis approach (due to paucity of available data), and the SAP will be updated to include additional analyses to assess adequacy of dosing during pregnancy as more information on the PK and pharmacodynamics of RDV in adults with COVID-19 becomes available.

For women who deliver within 5 days after receiving RDV, placental transfer will be assessed by comparing the drug concentrations of RDV and GS-441524 in plasma from cord blood with concentrations in maternal plasma at delivery using the GMR with a 90% CI.

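### Arm 2 sets no minimum time since delivery and requires no delivery date, so recently delivered women cannot be reliably identified in the comparison of pregnant with non-pregnant women

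*Protocol*

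**What the plan says.** Protocol 1.3 explains that women cannot serve as their own postpartum controls here, because treatment lasts only 5 to 10 days, and that the best comparison "would be data from non-pregnant adult women of childbearing potential". Arm 2 supplies that group.

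On pregnancy status, Arm 2 eligibility (4.2.4) asks only that a woman be "not suspected to be pregnant, based on participant report and/or investigator or designee determination". Sections 4.2 and 4.3 name no interval since delivery. The one route to exclusion is 4.3.5, a matter of investigator opinion, which covers conditions that would "complicate interpretation of study outcome data" but does not mention recent delivery.

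The protocol foresees postpartum women in Arm 2. Section 3 provides that "for women in both Arms who are lactating, and who consent to this sample collection, an optional breast milk sample may be collected". Section 6.5.2 describes the donors as postpartum ("an optional breast milk sample will be collected from postpartum lactating women who are still hospitalized"), although that sentence names no arm.

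On data, Table 2 in Section 6.3 lists "Arm 1: Prior pregnancy information (number and dates of prior pregnancies, outcome of prior pregnancies"), so that item is limited to Arm 1. The nearest item without an arm limit is "Last menstrual period". The Delivery period (6.6) also applies to Arm 1 only.

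On analysis, Section 9.6 compares the arms by a GMR and two one-sided tests, with equivalence shown when "the 90% CI of the GMR is between 0.7 and 1.43". It describes no exclusion, adjustment or sensitivity analysis for recent delivery. The comparison is an other objective (2.3.2), and SAP 2.3 leaves other objectives to separate SAPs.

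**The concern.** A woman sampled a day or two after delivery counts as an ordinary non-pregnant comparator, on the same footing as one who has never been pregnant. If her drug disposition is still partly that of pregnancy, the contrast between the arms shrinks and the GMR moves toward 1. In an equivalence test that is the anti-conservative direction, because it makes a claim of no more than a 30% difference easier to reach.

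The plan treats the time around delivery as relevant on one side only. SAP 5.1.1 lists onset of labor as an intercurrent event for the Arm 1 PK estimand. SAP 5.2.1, for Arm 2, lists only treatment discontinuation and death.

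Although the comparison ranks as an other objective, Protocol 9.4.1 calls it important if feasible, and the 30% question was used to choose 20 evaluable women per arm.

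**Working it through.** **Inputs from the documents.** 20 evaluable women per arm; CV 0.2, 0.3 or 0.4; 90% CI for the GMR to lie wholly within 0.70 to 1.43 (Protocol 9.4.1 and 9.6).

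**Inputs that are assumptions.** The number m of the 20 Arm 2 women who are recently delivered, and the share r of the log pregnancy effect that they keep. Neither is in the documents, so both are varied.

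**Step 1: reproduce the plan.** Log-scale SD = √ln(1 + CV²); at CV 0.3 this is √ln(1.09) = 0.294. With 38 degrees of freedom the t value is 1.686. An exact calculation of the two one-sided tests gives power at GMR 0.9 of 98.9%, 84.4% and 63.0% for CV 0.2, 0.3 and 0.4, as in Table 9. At a true GMR of 0.70 the pass rate is 5.0% at each CV, which is the nominal error.

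**Step 2: what a pass requires.** At CV 0.3 the half-width of the log CI is about 1.686 × 0.294 × √(2/20) = 0.157. The observed GMR must then be at least about 0.70 × e^0.157 = 0.82. A point estimate only just above 0.70 does not pass.

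**Step 3: the shift.** Expected GMR = true GMR^(1 − r·m/20). For a true GMR of 0.70, m = 4 and r = 1: 0.70^0.8 = 0.752.

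**Step 4: the pass rate at the margin.** Simulation, true GMR 0.70, CV 0.3, 20 versus 20, including the extra Arm 2 variance from the mixture:

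| Recently delivered in Arm 2 | Expected GMR, r = 1 | Passes, r = 1 | Expected GMR, r = 0.5 | Passes, r = 0.5 |
|---|---|---|---|---|
| 0 of 20 | 0.700 | 5% | 0.700 | 5% |
| 2 of 20 | 0.725 | 9% | 0.713 | 7% |
| 4 of 20 | 0.752 | 16% | 0.725 | 10% |
| 6 of 20 | 0.779 | 26% | 0.738 | 13% |

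With 4 of 20 and r = 1, the rate is 23% at CV 0.2 and 13% at CV 0.4. The upper margin (true GMR 1.43) behaves in the same way.

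**Step 5: where the effect vanishes or turns.** With r = 0 there is no shift. If postpartum PK overshoots the non-pregnant level (r = −0.5), 4 of 20 lowers the pass rate at 0.70 to about 2%. Further outside the margin the test still mostly fails. At a true GMR of 0.65, CV 0.3 and r = 1, it passes about 0.8%, 2%, 5% and 11% of the time with 0, 2, 4 and 6 such women. At 0.60 with 4 of 20 it passes under 1%.

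**The case against.** Several points on the other side stand.

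- **The bias is conditional.** Protocol 1.2 says the effect of pregnancy on hydrolase activity and RDV PK is unknown; its modelled increase in elimination concerns GS-441524. Section 1.3 reports that the predecessor study used postpartum women as their own controls, so the team regards postpartum sampling as a usable reference. It gives no interval after delivery, however, and without a date near and late postpartum women cannot be told apart.
- **Other data bear on it.** Table 2 records last menstrual period and conditions within 48 hours before the first infusion for both arms, and renal function and weight are candidate covariates in the population PK model (10.4.2). A reader might infer that time since delivery will be unknown and beyond any handling in analysis. That goes too far: these items help, but none is a delivery date, and none is required to reveal one.
- **The analysis plan for this test is not to hand.** Section 9.6 is a summary, and the SAP for the other objectives was not among the documents. It could still contain such an analysis, but it could not reliably use a date that was never collected.
- **Lean data collection and broad entry were deliberate** (1.3), and lactating women serve objective 2.3.6. This argues against a new exclusion, but much less against one abstracted date.
- **The evidence on who enters is limited.** Section 6.5.2 names no arm, and Arm 1 women may themselves deliver during the study. The firm support is the reference in Section 3 to both arms, and lactation does not by itself mean recent delivery.

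A reader might also take an expected GMR of 0.71 (true 0.65, 4 of 20 fully pregnancy-like) as a wrongly passed test. It is not, because the rule applies to the whole 90% CI and such a trial passes only about 5% of the time.

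**Conclusion.** The gap is real and small. The protocol allows recently delivered women into Arm 2 and does not require the date that would identify them, so their influence on the between-arm GMR cannot be reliably checked.

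The documents do not support the stronger statement that the equivalence test is biased toward passing. That requires a material number of such women who still have pregnancy-like PK, and neither is documented. Under that assumption, at the 0.70 margin with CV 0.3, the 5% error becomes about 7% to 26% across 2 to 6 women of 20 and half to full retention of the effect. It stays at 5% if PK has normalised and falls if it overshoots.

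The primary description of Arm 1 and the secondary description of Arm 2 do not use this test, and the Table 9 arithmetic is sound. For the Arm 2 summary, the only consequence is that its mix of recently delivered and other women would go unreported.

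**What to change.** 1. Add date of last delivery and lactation status for Arm 2 to Table 2, abstracted retrospectively from the chart where needed.
2. Report how many evaluable Arm 2 women were recently delivered.
3. In the separate SAP for the comparison, and before the PK data are compared, pre-specify a sensitivity GMR with 90% CI that excludes Arm 2 women within a cut-off interval after delivery. The protocol pharmacologists should set the interval.

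Eligibility and the Primary SAP need not change. The cost is one or two abstracted items and one further analysis, with a smaller Arm 2 in that run. At GMR 0.9 and CV 0.3, power falls from 84% (20 versus 20) to about 80% (20 versus 16).
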